3.7 Sensitivity analyses

Three sensitivity analyses of the primary outcome will be conducted. Firstly, an unadjusted analysis will be presented, which will present the odds ratio, 95% confidence interval and p-value from an unadjusted logistic regression model. Secondly, although very unlikely, a participant may be transplanted but then require a re-graft during the trial period (i.e. because their previous graft failed). Hence the participant may be randomised twice into the trial and there will not be independence between observations in the data (an assumption of the logistic regression model). If this situation does occur, then we will conduct a separate, second sensitivity analysis, which will utilise the model from the primary analysis but also include a nested random effect for participant in the logistic regression model, to assess for any effects of this. Thirdly, the definition of acute hyponatraemia will be expanded to include plasma or blood gas sodium concentration <135mmol/L. This will be analysed using a mixed logistic regression model adjusting for donor type (living vs deceased donor), participant weight (<20kg vs ≥20kg pretransplant) and transplant centre as a random effect. The number and percentage of participants who experience acute hyponatraemia will also be presented by whether the event occurred in plasma or blood gas by trial arm and overall, alongside the median and interquartile range of the number of each event experienced.

For the secondary outcome of other electrolyte abnormalities within the first 72 hours post transplantation, their definitions will also be expanded to include blood gas results. As magnesium is only collected in plasma, hypomagnesaemia will not be included in these sensitivity analyses. The numbers and percentage of participants who experience each of these events will also be presented by whether the event occurred in plasma or blood gases by trial arm and overall, alongside the median and interquartile range of the number of each event experienced. No further statistical testing will be conducted.

Statistical Analysis Plan

- Hypernatraemia (defined as sodium concentration > 145mmol/l)
- Hyperkalaemia (defined as potassium concentration > 5.5mmol/L)
- Hypokalaemia (defined as potassium concentration < 3.5mmol/L)
- Non anion-gap acidosis (defined as bicarbonate < 20mmol/L and anion gap < 20mmol/L. Anion gap will be calculated as the sum of sodium and potassium, minus the sum of chloride and bicarbonate)
- Hyperglycaemia (defined as glucose > 5.5 mmol/L)
- Hyperchloraemia (defined as chloride concentration > 107mmol/L)
- Excessive rate of reduction in sodium concentration (defined as >1mmol/L/hour averaged over 6 hours)
- Excessive magnitude of reduction in sodium concentration (defined as > 10mmol/L from pre-transplant level)

Where multiple test results are required to meet the criteria for an abnormality, events will only be identified in either all plasma results or all blood gas results (e.g. determining an excessive magnitude of reduction in sodium concentration will compare plasma sodium results against the pre-transplant plasma sodium, and blood gas sodium results against the pre-transplant blood gas sodium).

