1.6 Sample size calculation

The sample size required for this trial is 144 participants randomised. Analysis of 76 paediatric transplants performed at Great Ormond Street Hospital between 1 January 2015 and 31 March 2018 showed that 45 children (59%) experienced hyponatraemia within the first 72 hours post-transplant when managed with 0.45% saline 5% glucose fluid (1). This was used as the baseline rate. In the Cochrane systematic review by McNab S et al. (2), a 50% reduction in risk of hyponatraemia was shown. A greater effect size is anticipated because the rate of fluid delivery to children following kidney transplant significantly exceeds maintenance requirements (3). Using the 50% effect size from the Cochrane review, the assumed incidence of hyponatraemia would be reduced to 29.5%. A two-sided test with 90% power, 5% type I error and 1:1 allocation and allowing for two formal interim analyses for harm or benefit would require 128 patients. After allowing for 10% drop out, for example if a transplant cannot proceed due to a positive cross match, the total number of participants required is 144.

2. Data Handling

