4.1.4 Participants entered in trial more than once and co-enrolled in other trials

| Table XX Participants entered into the trial more than once | | | | | | |
|---|---------------|------------------|--------|--------------------------------|--|--|
| Randoi numbe | misation r | Rando treatme | | Reason for multiple enrolments | | |
| First | Second | First | Second | | | |
| | | | | | | |
| | | | | | | |
| | | | | | | |

| Table XX Participants co-enrolled during the trial | | | |
|--|----------------------|---------------------------------|--|
| Randomisation number | Randomised treatment | Names of the co-enrolled trials | |
| | | | |
| | | | |
| | | | |

Statistical Analysis Plan

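### The planned check for children randomised twice (SAP 3.7) will reprint the primary odds ratio whatever the truth, because the participant variance is not identified in practice

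*SAP*

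**What the plan says.** Section 3.7 recognises that a failed graft may lead to a second transplant within the trial: "Hence the participant may be randomised twice into the trial and there will not be independence between observations in the data". If this happens, the second of three sensitivity analyses keeps the primary model and will "also include a nested random effect for participant in the logistic regression model, to assess for any effects of this". Table 4.7 reserves a row for the resulting odds ratio, confidence interval and p-value.

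Four other parts of the SAP bear on this:

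- Section 3.2 analyses everyone randomised and transplanted, by allocated arm, so both entries of a re-grafted child stay in the primary analysis.
- Section 3.2 also says that mixed models will be estimated by pseudo-likelihood. Its model-reduction steps are triggered by separation only.
- Section 3.3 defines one binary outcome per transplant: any plasma sodium below 135 mmol/L within 72 hours.
- Section 4.1.4 has a table headed "Participants entered into the trial more than once", with first and second columns for randomisation number and for treatment. It has no column for outcome.

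**The concern.** A random intercept for participant is estimated from how alike the repeated outcomes of the same child are. By the SAP's own account hardly any child will have repeated outcomes. A child with a single 0/1 result gives no practical information on how much of the variation is between children, so the term rests on the one or two children who enter twice.

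At stake is the meaning of the sensitivity result. A reader of table 4.7 will see an odds ratio from a model that claims to allow for double entry. If it matches the primary one, the natural conclusion is that double entry was tested and made no difference. If the model would give that match whatever the dependence within a child, the conclusion has no basis. The separation rules in 3.2 do not help, because a participant variance that is near zero or not identified is not separation.

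**Working it through.** **Planning figures.** Section 1.6 reports that an analysis of 76 transplants "showed that 45 children (59%) experienced hyponatraemia within the first 72 hours post-transplant" (45/76 = 59%). Halving gives 59% × 0.5 = 29.5%, as stated: "the assumed incidence of hyponatraemia would be reduced to 29.5"%. The evaluable number also stands: "two formal interim analyses for harm or benefit would require 128 patients". A fixed design at 90% power needs 116 (pooled variance) or 130 (continuity-corrected). A simulated O'Brien-Fleming design with looks at 70, 100 and 128 multiplies these by 1.022, giving about 119 or 133, and 128 lies between. With 10% drop-out, 128/0.9 = 142.2, so 143, or 144 as the next even number.

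**Illustrative data.** 128 records, 64 per arm. Events: 64 × 0.59 = 37.8, taken as 38 (control); 64 × 0.295 = 18.9, taken as 19 (Plasma-Lyte). Odds ratio = (19/45)/(38/26) = 494/1710 = 0.289. Site, weight and donor type are left out. One repeat child is assumed, since the SAP gives no expected number.

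**Step 1: why single outcomes are uninformative.** With participant SD σ, the chance of an event for a child seen once is the average of expit(η + σu) over a standard normal u. For any σ, η can be chosen in each arm to give exactly 38/64 and 19/64. With no repeats, −2 log L is therefore 164.31 at every SD from 0 to 8. Exact flatness belongs to this two-group model; with the planned covariates the statement is that the variance is not identified in practice.

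**Step 2: one repeat child, full likelihood.**

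| Repeat child | −2 log L, SD 0 | SD 2 | SD 8 |
|---|---|---|---|
| Event at both entries, one per arm | 164.31 | 163.59 | 163.26 |
| No event at either entry, one per arm | 164.31 | 163.83 | 163.60 |
| Event on control, none on Plasma-Lyte | 164.31 | 164.71 | 164.97 |
| None on control, event on Plasma-Lyte | 164.31 | 166.26 | 173.49 |

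In the first three rows the fit changes by about 1 or less over the whole range. Only the last pattern argues against large values, and its best fit is at SD 0. In simulated trials with one repeat child (60 per setting), the maximum-likelihood SD fell on a boundary (0, or the grid limit of 8) in 92% to 97%, whether the true SD was 0, 1 or 2. With three repeat children it was still 78% to 85%.

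**Step 3: the method the SAP specifies.** Pseudo-likelihood compares the spread of the working residuals with the binomial variance. For children seen once, the squared Pearson residuals in an arm of size n with event proportion p sum to n·p(1−p)/[p(1−p)] = n, so there is no excess to attribute to participants. Refitting the data above by pseudo-likelihood, residual and maximum-likelihood type, scale fixed at 1:

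| Repeat child | Estimated variance | Odds ratio |
|---|---|---|
| Same outcome twice, one entry per arm | 0.05 to 0.15 | 0.289 |
| Different outcomes, one entry per arm | 0 to 0.03 | 0.289 |

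In simulated trials (25 per setting) with one or three repeat children, the median estimated variance was 0.12 to 0.24 whether the true variance was 0 or 4. The log odds ratio was 1.00 to 1.01 times the primary one (10th to 90th percentile).

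**Step 4: what dropping the second entry would show.** Removing one record from the illustrative data gives:

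- Plasma-Lyte event: (18/45)/(38/26) = 0.274
- Plasma-Lyte non-event: (19/44)/(38/26) = 0.295
- control event: (19/45)/(37/26) = 0.297
- control non-event: (19/45)/(38/25) = 0.278

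Against 0.289 these are changes by a factor of 1.02 to 1.06. In the simulated trials the median factor was 1.03 with one re-entered child (largest 1.10), and 1.04 to 1.06 with three (largest 1.18).

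**The case against.** The strongest reply is that the planned check is harmless. It runs only if a re-graft occurs, leaves the primary estimate and p-value alone, and with one or two children among about 128 the dependence cannot move the answer much. Reprinting the primary odds ratio is then close to the truth, and a first-entry analysis would lead to the same conclusion. This stands, and it is why the point is minor. It does not save the check: agreement that was bound to appear is not evidence.

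A second reply is that section 3.7 aims only at non-independence, not at carry-over from the first allocation. That also stands, but the participant term does not assess non-independence either: its estimate was much the same with a true variance of 0 or 4.

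A reader might infer that one concordant repeat child would make the trial publish an extreme odds ratio. Under full maximum likelihood that can happen: with an event at both entries the odds ratio moves from 0.289 at SD 0 to 0.13 at SD 2 and 0.002 at SD 8 while the fit slightly improves. But section 3.2 specifies pseudo-likelihood, under which those values would not be printed.

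A reader might also see a defect in the possibility that one child counts in both arms. Nothing in the SAP ties the second allocation to the first, but independent randomisation of a new transplant is not in itself an error.

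**Conclusion.** The point holds in a limited form. The second sensitivity analysis in 3.7 cannot meet its stated purpose, because the participant variance is not identified in practice. Fitted as the SAP specifies, it will essentially repeat the primary odds ratio whether or not a child's outcomes are correlated.

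The consequence is false reassurance in one conditional row of table 4.7. The documents do not support a claim that the primary result is at risk: with one re-entered child, leaving out the second entry changed the odds ratio by a median factor of 1.03.

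The figures assume the planning rates, 128 analysed records and one to three repeat children. The illustrative fits omit site, weight and donor type; the simulated fits omit site. The conclusion depends on re-entry being rare, as the SAP itself expects.

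**What to change.** In section 3.7, replace the second sensitivity analysis with the primary model fitted to each participant's first randomised transplant only, and delete the nested participant random effect. This makes children independent of one another, needs no extra variance term, and shows directly what the second entries contribute.

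Relabel the matching row of table 4.7. In the multiple-entry table of section 4.1.4, which already lists both allocations, add the primary outcome at each entry.

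The cost is one sentence, one row label and one pair of columns. The sensitivity analysis loses the few second entries; the primary analysis is unchanged.

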3.8 Procedures for handling Missing Data

Any missing primary and secondary outcome data will be summarised. For the primary outcome and other blood test results, the result will be considered missing if there are no results for that measurement within the 72-hour period post transplant. It is anticipated that missing data for the primary outcome will be rare, as the plasma sodium measurement is also used to determine one of the key SAEs within the trial, which mandates immediate reporting. Missing data due to death or withdrawal are also anticipated to be very rare: data from the UKTR showed that the 1-year patient survival rate for those transplanted between 2015-2018 was 99% (95% confidence interval 96-100) for paediatric kidney transplants from living and DBD donors (5). Primary and secondary outcome measures will not be imputed and these will be treated as missing data and excluded from the relevant analyses. If outcome data is missing for more than 25% of participants, outcomes will not be reported.

To explore if missing values have an undue impact on the primary outcome result, a sensitivity analysis using multiple imputation will be performed if the primary outcome is missing in more than 5% of the participants included in the modified intention to treat analysis. Variables will be included in the imputation model if they have a completeness of ≥65% and these variables are:

- Donor: type, age, ethnicity, BMI
- Trial participant/Recipient: age, sex, ethnicity, cause of end stage kidney disease, native urine output, dialysis type, weight and height at transplant, systolic blood pressure, blood group, calculated reaction frequency, graft number
- Transplant: blood group match, transplanting centre, cold ischaemic time, HLA mismatch between donor and recipient, graft placement.

Forty imputations will be used and the average across the imputations will be calculated. The model specified in section 3.3 will be utilised.

If the proportion of participants with a missing primary outcome is less than or equal to 5% then this sensitivity analysis will not be performed.

Statistical Analysis Plan

All the risk adjustment factors will always be known, as weight and site are required for randomisation and donor type is mandatory data required by the UKTR.

4. Data Analysis Tables

Data analysis will be based on the following tables.

- 4.1 Screening, Recruitment and Follow-up tables
 - 4.1.1 Recruitment by Centre

| Table XX Re | ecruitment b | y Centre | | | | |
|-------------|-----------------------------|--------------------|---------------------|---------------------------------|----------------------|-----------------------|
| Site | Total number screened | Number eligible | Number consented | % consented from eligible | Number randomised | % rand. from eligible |
| Belfast | | | | | | |
| Birmingham | | | | | | |
| Bristol | | | | | | |
| GOSH | | | | | | |
| Evelina | | | | | | |
| Leeds | | | | | | |
| Manchester | | | | | | |
| Newcastle | | | | | | |
| Nottingham | | | | | | |

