3.3 Analysis of primary outcome measures

The number and percentage of participants who experience acute hyponatraemia (defined as plasma sodium concentration <135mmol/L) within 72 hours post-transplant will be presented by trial arm and overall. This will be analysed using a mixed logistic regression model adjusting for donor type (living vs deceased donor), participant weight (<20kg vs ≥20kg pre-transplant) and transplant centre as a random effect. A superiority hypothesis will be tested and the results from the adjusted analysis will be considered the primary analysis. The adjusted odds ratio for treatment, with 95% confidence interval, will be presented from this model, with the p-value from the likelihood ratio test when including and excluding the treatment term from the model. This will be the primary analysis. The median and interquartile range of the number of each event experienced by each participant will also be presented, but no further statistical testing will be conducted on these. As outlined above, this will be analysed using the modified intention to treat population, which includes all participants randomised and transplanted. This outcome will also be analysed in the per protocol population, which additionally excludes those randomised in error, with a protocol deviation, or withdrawn from the trial.

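### The imputation model for the missing-data sensitivity analysis leaves out randomised arm, so its odds ratio is pulled towards 1

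*SAP*

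**What the plan says.** SAP section 3.8 does not impute outcomes in the main analyses. It adds a multiple-imputation sensitivity analysis "if the primary outcome is missing in more than 5% of the participants included in the modified intention to treat analysis". Above 25% missing, outcomes are not reported, so the imputed result can appear only between just over 5% and 25%. The primary outcome is missing when a participant has no plasma sodium result in the 72 hours after transplant.

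The imputation model is specified by name: "Variables will be included in the imputation model if they have a completeness of ≥65% and these variables are", and then three groups:

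- "Donor: type, age, ethnicity, BMI"
- for the recipient, "age, sex, ethnicity, cause of end stage kidney disease, native urine output, dialysis type, weight and height at transplant, systolic blood pressure, blood group", plus calculated reaction frequency and graft number
- "Transplant: blood group match, transplanting centre, cold ischaemic time, HLA mismatch between donor and recipient, graft placement"

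The section then says: "Forty imputations will be used and the average across the imputations will be calculated. The model specified in section 3.3 will be utilised". In section 3.3 that model is a mixed logistic regression on treatment, donor type, weight group and centre, and its target is treatment: "The adjusted odds ratio for treatment, with 95% confidence interval, will be presented from this model".

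**The concern.** An imputation model should contain every term of the analysis model that will be fitted to the imputed data. Here one term is absent, and it is the one whose coefficient is being estimated. Donor type, weight and centre are all listed; arm is not, and nothing says that imputation is done within arm.

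If arm is left out, the imputed values carry almost no treatment effect. Mixing them with observed values dilutes whatever effect the observed values show. The purpose of the analysis is to show whether missing values distort the primary result. As specified, it produces a shift of its own even when the complete cases are unbiased, and a reader could take that shift as evidence that missing data matter.

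**Working it through.** **Does the list carry arm indirectly?** The 21 listed variables (4 donor, 12 recipient, 5 transplant) are baseline, donor or surgical factors. I read systolic blood pressure as the baseline value, since it stands in the baseline table in section 4.2. Randomisation makes such variables essentially independent of arm, so none can stand in for it. The sentence invoking section 3.3 follows the one on averaging and reads as the analysis step; it does not put arm into the imputation step.

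**Inputs.** From section 1.6: control rate 0.59, Plasma-Lyte rate 0.295, 1:1 allocation, 128 evaluable participants. From section 3.8: 40 imputations; the result is produced only above 5% and up to 25% missing. The SAP gives no figure for the effect of imputation, so there is none to reproduce.

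**Design odds ratio.** (0.295/0.705) / (0.59/0.41) = 0.4184/1.4390 = 0.291.

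**Expected odds ratio with arm omitted.** Let a fraction m be missing at random, equally in both arms, with no covariate effects. Missing outcomes are then drawn at the pooled rate (0.59 + 0.295)/2 = 0.4425, and each arm's rate after imputation is (1 − m) × arm rate + m × 0.4425.

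- m = 6%: control 0.94 × 0.59 + 0.06 × 0.4425 = 0.5812; Plasma-Lyte 0.94 × 0.295 + 0.06 × 0.4425 = 0.3039; odds ratio 0.4365/1.3875 = 0.315.
- m = 10%: 0.5753 and 0.3098; odds ratio 0.331.
- m = 20%: 0.5605 and 0.3245; odds ratio 0.377.
- m = 25%: 0.5531 and 0.3319; odds ratio 0.401.

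The log odds ratio shrinks by 6.4%, 10.6%, 21.0% and 26.1% respectively. If all the missingness fell in one arm, the odds ratio would be 0.314 or 0.318 (depending on the arm) at 6% missing overall, and 0.433 or 0.451 at 25%.

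**Simulation check.** 4,000 trials of 64 per arm, outcomes missing completely at random, 40 imputations, Rubin's rules, no covariates, nominal two-sided 5% test:

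| Missing | Odds ratio, complete cases | Odds ratio, arm included | Odds ratio, arm omitted | Share p<0.05, arm included | Share p<0.05, arm omitted |
|---|---|---|---|---|---|
| 6% | 0.286 | 0.286 | 0.310 | 0.904 | 0.879 |
| 10% | 0.280 | 0.280 | 0.321 | 0.907 | 0.860 |
| 25% | 0.279 | 0.279 | 0.391 | 0.837 | 0.644 |

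With arm in the imputation model the complete-case answer is recovered at each level. Without it, the estimate moves towards 1 by about the calculated amount.

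**The case against.** **It may never run, and the pull is small where it would most likely run.** This stands. These are inpatients with routine sampling, and section 3.8 expects missing primary outcomes to be rare. Just above the trigger the odds ratio moves only from 0.291 to about 0.315. One of the reasons given for rarity is weaker than it looks: section 3.8 relies on immediate reporting of a sodium-based serious adverse event, while section 3.5 says sites no longer had to report electrolyte events after protocol v2.0. Central collation of blood results (section 2.2) may still keep missingness low. None of this makes the listed model right if the analysis is triggered.

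**Stronger readings that the SAP does not support:**

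- *Leaving out sodium also causes the pull.* It does not. Pre-transplant and blood gas sodium are plausible predictors of the missing outcome, and omitting them loses information and makes missing at random harder to defend. The pull towards 1 comes from omitting arm. Whether a blood gas exists when plasma sodium is wholly absent is not known from the SAP.
- *The interval will be too narrow and p-values will be averaged.* Section 3.8 says "Forty imputations will be used and the average across the imputations will be calculated", which describes the usual pooled point estimate. It does not say that variances or p-values are averaged. The likelihood ratio footnote in the section 4.7 table is compatible with a pooled likelihood ratio test. The wording is terse, but no error is shown.
- *The imputation model will separate.* Twenty-one variables is a long list against about 57 expected events (0.4425 × 128), but the SAP names no imputation method, and separation has not been demonstrated.
- *Nothing else in the plan bears on missing plasma sodium.* The third sensitivity analysis in section 3.7 accepts blood gas sodium as well as plasma, and can bring in participants with only a gas result. It is not presented as a missing-data analysis, so it is a partial answer.

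**Conclusion.** The imputation specification in section 3.8 is wrong as written. Followed literally, it biases the treatment odds ratio of this sensitivity analysis towards 1: from 0.29 to about 0.315 at 6% missing, 0.33 at 10% and 0.40 at 25%. The sizes rest on the design event rates, equal missingness at random within arm and no covariate effects. Other rates or patterns would change the size; the direction stays towards no effect as long as the observed outcomes show a difference between arms.

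The reach is limited. A reader might infer that the primary result is at risk; it is not, because the primary analysis uses no imputed values. Nor is the sensitivity analysis useless over its whole range: near the 5% trigger the distortion is slight, and it becomes material towards 25%.

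**What to change.** In section 3.8, add randomised arm to the imputation variables, exempt from the completeness rule, or state that imputation is done separately by arm. This alone removes the pull.

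Two secondary improvements can go into the same edit: add pre-transplant plasma sodium and, where available, blood gas sodium from the 72 hours as predictors; and state that log odds ratios and their variances are combined by Rubin's rules, naming the pooled test behind the p-value in the section 4.7 table.

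The cost is a few lines of SAP wording. Arm is known for every participant, and the blood results are already being collected. Sample size, the primary analysis and trial conduct do not change.
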